 - Note: For subjects with a TFC score of 8-13 at Screening who did not require an LAR to provide informed consent, the caregiver must attend the following visits: Screening, Baseline, Weeks 4, 8, 15, 28 and visits every 13 weeks thereafter through the End of Treatment visit. Caregivers will be encouraged to attend other visits.
 10. Subject is able to ambulate without assistance for at least 20 yards (Note: The use of assistive devices (i.e., walker, cane) are permitted during ambulation).
 11. Has sufficient reading skills to comprehend the subject completed rating scales.

4.3 *Exclusion Criteria*

Subjects meeting any of the following criteria will be excluded:

1. Subject has a serious untreated or undertreated psychiatric illness, such as depression, at Screening or Baseline.
 - Note: Subjects receiving antidepressant therapy may be enrolled if on a stable dose for at least 8 weeks before Screening (See Appendix 12) for prohibited antidepressants).
2. Subject has active suicidal ideation at Screening or Baseline.
3. Subject has history of any of the following suicidal thoughts or behavior at Screening or Baseline:
 - Previous intent to act on suicidal ideation with a specific plan (positive answer to question 5 on C-SSRS), irrespective of level of ambivalence at the time of suicidal thought
 - Previous preparatory acts or behavior
 - A previous actual, interrupted or aborted suicide attempt
4. Subject has a score ≥ 11 on the depression subscale of the Hospital Anxiety and Depression Scale (HADS) at Baseline.
5. Subject has an unstable or serious medical or psychiatric illness at Screening or Baseline.
6. Subject has received tetrabenazine within 7 days of Baseline (Rollover subjects).
7. Subject has received any of the following concomitant medications within 30 days of Screening or Baseline:
 - Antipsychotics (See [Appendix 13](#))
 - Metoclopramide
 - Monoamine oxidase inhibitors (MAOI)
 - Levodopa or dopamine agonists

- Reserpine
 - Amantadine
 - Memantine (Rollover subjects only)
 - Switch subjects may receive Memantine if on a stable, approved dose for at least 30 days.
8. Subject has a score of ≥ 11 on the Swallowing Disturbance Questionnaire (SDQ) at Screening or Baseline.
9. Subject has a Unified Parkinson's Disease Rating Scale (UPDRS) dysarthria score of ≥ 3 at Screening or Baseline.
10. Subject requires treatment with drugs known to prolong the QT interval. Note:
- Quetiapine (Seroquel) is not allowed.

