6.7.8 Swallowing Disturbance Questionnaire (SDQ)

The Swallowing Disturbance Questionnaire is a self-administered questionnaire comprised of 15 questions that assess frequency of swallowing disturbance (20). It has been validated in subjects with Parkinson’s disease and has been shown to be a sensitive and accurate tool for identifying subjects with swallowing disturbances arising from different etiologies. A sensitivity and specificity analysis demonstrated that a threshold score of 11 was the optimal score for identifying subjects with dysphagia that had underlying pathology confirmed on fiberoptic endoscopic evaluation of swallowing (FEES) (21).

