7.3.8 Swallowing Disturbance Questionnaire (SDQ)

The SDQ is a self-administered questionnaire comprising 15 questions that assess the frequency of swallowing disturbance. Scores range from 0.5 (normal) to 44.5 (severe impairment).

8 Statistical Methods

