9.9.7 Other Safety Assessments

Other safety outcomes include the following:

- HADS (HADS Anxiety subscale [HADS-A] score and HADS Depression subscale [HADS-D] score)
- C-SSRS

-
- MoCA[®] (total score)

 - UHDRS
 - Parkinsonism subscore
 - Verbal fluency test score,
 - Symbol digit modalities test score
 - Stroop interference test scores of the cognitive exam, including raw color naming score, raw word reading score, raw interference score, as well as the adjusted interference score¹. The adjusted interference score can be calculated by subtracting a “predicted score”, calculated as (raw color naming *raw word reading)/(raw color naming + raw word reading), from the raw interference score.
 - Behavioral assessment item scores (the product of frequency and severity) (depressed mood, apathy, low self-esteem/guilt, suicidal thoughts, anxiety, irritable behavior, disruptive or aggressive behavior, perseverative/obsessional thinking, compulsive behavior, delusions, hallucinations), behavioral assessment total score (sum of frequency × severity item scores)
 - Functional assessment score
 - Independence scale score
 - Total functional capacity (TFC) score
 - Question 78 and 79 scores of the clinical summary section (Part VII)]

 - UPDRS dysarthria (speech score)

 - SDQ (total score)

 - BARS (summary score and global clinical assessment of akathisia score)

 - ESS (total score)

 - Duration of time to achieve a stable dose of SD-809

For all quantitative data (which includes all of these assessments except for the C-SSRS and the Question 78 and 79 scores of the UHDRS), except the duration of time to achieve a stable dose of SD-809, descriptive statistics will be presented by visit for the actual data and for the changes from baseline. For the ESS total score, SDQ, UPDRS (speech) and the BARS scores, 95% confidence intervals will be presented for the true mean changes from baseline. Descriptive statistics (and 95% confidence intervals for the true mean changes from Week 8 for the ESS total

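### SAP 9.9.7 summarises SDQ, HADS-Depression and UPDRS speech only as continuous scores; no count of subjects newly reaching the entry limits is planned, so new cases are counted only if reported as adverse events

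*SAP*

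**What the plan says.** SAP 9.9.7 lists the HADS subscales, the UPDRS speech score and the SDQ total among the other safety outcomes. Each is summarised by visit, as observed values and as change from baseline and from Week 8. SAP 8.7 defines the statistics for continuous data: number of observations, mean, SD, median, minimum and maximum. Intervals are added for some scales: after naming the ESS total, the SAP continues "SDQ, UPDRS (speech) and the BARS scores, 95% confidence intervals will be presented for the true mean changes from baseline". HADS has no such interval.

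Protocol 4.3 sets entry limits on the same three scales:

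- SDQ: "Subject has a score of ≥ 11 on the Swallowing Disturbance Questionnaire (SDQ) at Screening or Baseline"
- HADS-D: "Subject has a score ≥ 11 on the depression subscale of the Hospital Anxiety and Depression Scale (HADS) at Baseline"
- UPDRS speech: "dysarthria score of ≥ 3 at Screening or Baseline"

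Only the SDQ value has a clinical meaning in the protocol. Section 6.7.8 reports that "a threshold score of 11 was the optimal score for identifying subjects with dysphagia" whose underlying pathology was confirmed endoscopically. HADS-D 11 and dysarthria 3 appear solely as eligibility limits.

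Elsewhere the SAP does count subjects: above QTcF limits (9.9.5), moving between laboratory categories (9.9.6), and with any post-baseline suicidal ideation or behaviour (9.9.7). SAP 9.9.1 plans per-subject frequencies of treatment-emergent adverse events by preferred term. It also plans exposure-adjusted rates for all preferred terms and for grouped events, including Dysphagia and Depression.

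**The concern.** This is a long-term safety study, and Protocol 3.2 says some of its safety evaluations were chosen to target known effects of the drug class. Eligible subjects start below SDQ 11, HADS-D 11 and dysarthria 3, so the natural question is how many reach those values on treatment. No planned table answers it. A mean and its interval describe the average shift, and a maximum shows that someone crossed. Neither gives the number of people, or whether the same person is above the limit at successive visits.

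The scale ratings also cannot be set beside the adverse event rates as a second, systematically collected view of the same problem, so under-reporting of dysphagia or low mood as adverse events would not be visible.

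**Working it through.** The plan states no figure on this point, and its sample size has no statistical basis (Protocol 8.5), so there is no calculation to reproduce. Planned numbers are about 80 Rollover and 36 Switch subjects (Protocol 3), 116 in all.

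**1. How far the mean can hide a minority.** Assumptions, none from the documents: a fraction f of subjects worsens by d SDQ points, the rest change by r, and the within-group SD of change is s.

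- Mean change = f·d + (1−f)·r
- Variance = s² + f(1−f)(d−r)²
- 95% CI = mean ± t·√(variance/n)

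Rollover, n = 80, 8 subjects worsen by 8 points (f = 0.10):

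| Rest change by | s | Mean change | 95% CI |
|---|---|---|---|
| 0 | 2 | 0.80 | 0.10 to 1.50 |
| 0 | 4 | 0.80 | -0.24 to 1.84 |
| -1 | 2 | -0.10 | -0.85 to 0.65 |
| -1 | 4 | -0.10 | -1.17 to 0.97 |

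Third row in full: 0.10 × 8 + 0.90 × (−1) = −0.10; variance = 4 + 0.09 × 81 = 11.29; half-width = 1.99 × √(11.29/80) = 0.75.

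Switch, n = 36, 4 subjects worsen by 8 points, s = 2: mean 0.89 (-0.20 to 1.98) if the rest are unchanged, and 0.00 (-1.17 to 1.17) if the rest improve by 1.

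**2. What a count would show for the same subjects** (Clopper-Pearson 95% CI, taking every worsened subject to cross): Rollover 8/80 = 10.0% (4.4 to 18.8%); Switch 4/36 = 11.1% (3.1 to 26.1%).

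**3. What the planned maximum shows.** If each subject has a 5% chance of being at or above 11 at a visit, the chance that the visit maximum reaches 11 is 1 − 0.95⁸⁰ = 98% for n = 80 and 1 − 0.95³⁶ = 84% for n = 36. It signals a crossing but not how many.

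**4. How much of a count would be noise.** Assume normal SDQ scores with untruncated mean 6, SD 4 and test-retest correlation 0.9 to 0.6, no true change, the cap of 11 applied at Screening and Baseline, and six later ratings. The schedules give five SDQ ratings by Week 28 and a sixth at Week 41. Simulated share of subjects at or above 11:

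| Summary | Correlation 0.9 | Correlation 0.6 |
|---|---|---|
| At any of six ratings | 8% | 21% |
| At a given visit | 2% | 5% |
| At two consecutive ratings | 2% | 4% |

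An any-time count can thus reach 10% without any real change. By-visit and confirmed counts are much less exposed.

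**The case against.** The strongest reply is that the information is largely in the plan already. A reader might infer that the SAP reports these scales only as mean changes. It does not: observed values, SD, median, minimum and maximum are tabulated by visit, and SAP 8.7 promises subject listings of all eCRF data. A reader might also infer that new dysphagia or depression is averaged away. That goes too far, because both are grouped adverse events of interest with per-subject exposure-adjusted rates.

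Nor do those rates rest on spontaneous reports alone. Protocol 7.3 has subjects and caregivers asked at every visit and telephone contact, and Protocol 6.6.8 lets staff detect events through other assessments. These points stand, and they limit the concern to a missing summary.

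The adverse event tables are still only partial cover:

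- Crossing a limit is not automatically an adverse event. The relevant example in Protocol 7.1.1 covers abnormal safety assessments that lead to a dose change, discontinuation or therapeutic intervention.
- The Dysphagia group has two preferred terms. The Depression group takes only terms containing that word. Dysarthria has no group.
- Under SAP 8.9 an unscheduled rating enters the by-visit tables only where the scheduled record is missing. Protocol 6.5 permits unscheduled SDQ, HADS and dysarthria ratings for intercurrent events, so a crossing seen then may be absent even from the maximum.

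A second reply is that crossings are hard to interpret. Switch subjects are on tetrabenazine at baseline. Rollover subjects may have crossed during C-15 and recovered in washout. The disease progresses and there is no control arm. This stands too: the count is of crossings new since the C-16 baseline, whatever their cause.

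It is tempting to add that capping scores at entry makes the mean tables unreadable through regression to the mean. Under the assumptions in step 4 that drift is only about 0.1 to 0.3 points, and the same mechanism inflates an any-time count more. It is no argument against the mean tables.

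**Conclusion.** The gap is real but modest. For three scales with fixed entry limits, the SAP gives continuous summaries and no number of subjects who newly reach the limit, so new cases are counted only through adverse event reporting. The case is strongest for SDQ, where the protocol itself gives 11 a clinical meaning. A reader might take all three limits as clinical cut-offs. The documents do not support that for HADS-D 11 or dysarthria 3, though using them avoids choosing a value after the data are seen.

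In the illustration, about 10% of Rollover subjects worsening by 8 points gives a mean change between -0.10 and 0.80, and in three of the four rows the interval includes zero. This depends on the assumed size of worsening, the change in the other subjects and the SD. With the rest unchanged and SD 2, the interval excludes zero, so the mean does not always hide such a group. The study is descriptive, with no formal tests (SAP 8.1), so no error rate or sample size is affected.

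**What to change.** In SAP 9.9.7 add one table by cohort, restricted to subjects below the relevant limit at baseline:

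- Number and percentage at or above SDQ 11 (main), HADS-D 11 and UPDRS speech 3 at each visit, among those rated.
- Number whose crossing is confirmed at the next rated visit, with crossings at the last on-treatment rating shown separately because they cannot be confirmed.
- Any-time counts, including unscheduled on-treatment ratings, only beside the two items above.

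Keep the existing continuous summaries. Label HADS-D 11 and speech 3 as entry limits rather than diagnostic cut-offs.

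The cost is one table from data already collected, using values already in the protocol. Two limitations belong in its footnote. Any-time counts grow with the number of ratings and through measurement noise (about 8-21% over six SDQ ratings under the stated assumptions, and more over longer follow-up). Without a control arm, crossings describe incidence and cannot be attributed to the drug.

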6.7.2 Columbia Suicide Severity Rating Scale (C-SSRS)

The Columbia Suicide Severity Rating Scale (C-SSRS) is an FDA endorsed questionnaire to screen for suicidality in trials of central nervous system (CNS) active compounds (15, 16). The C-SSRS is an interview by trained study personnel that should be done at Baseline and during the study as outlined in the Schedule of Events. The form provided at Screening collects the history of suicide (C-SSRS form version termed “baseline”) and subsequent visits use a C-SSRS termed “Since the Last Visit”.

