- Number of subjects with on-treatment QTcF values > 450ms, > 480ms, > 500ms
- Observed values and changes in UHDRS, UPDRS (dysarthria), BARS, HADS, ESS, C-SSRS, and MoCA©
- Duration of time to achieve stable doing of SD-809 ER

8.5 *Sample Size*

Because this is an open label safety study, the sample size is not based on statistical considerations.

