7.2 Safety Endpoints

Safety and tolerability will be assessed throughout the study by monitoring the following:

- Incidence of adverse events (AEs), serious AEs (SAEs), severe AEs, drug-related AEs, and AEs leading to withdrawal during the following periods:
 - The entire post-baseline period
 - During the Titration Period (from Day 1 to the end of Week 8) in Rollover subjects
 - During the Dose-Adjustment Period (from Day 1 to the end of Week 4) in Switch subjects
 - During the Extended Dose-Adjustment Period (from Day 1 to the end of Week 8) in Switch subjects who undergo dose adjustment between Weeks 4 and 8 (if at least 10% of Switch subjects have had a dose adjustment between Week 4 and Week 8)
 - During the Stable-Dose Period (Week 8 to end of study)
- Observed values and changes from baseline in clinical laboratory parameters (hematology, chemistry, and urinalysis)
- Observed values and changes from baseline in vital signs
- Observed values in ECG parameters and abnormal findings

- Numbers of subjects with QTcF values > 450 msec, > 480 msec, > 500 msec
- Counts and percentages for Columbia Suicide Severity Rating Scale (C-SSRS)
- Observed values and changes from baseline in the following:
 - Unified Huntington Disease Rating Scale (UHDRS)
 - Unified Parkinson's Disease Rating Scale (UPDRS) (dysarthria)
 - Barnes Akathisia Rating Scale (BARS)
 - Hospital Anxiety and Depression Scale (HADS)
 - Epworth Sleepiness Scale (ESS)
 - Montreal Cognitive Assessment (MoCA[®])
 - Swallowing Disturbance Questionnaire (SDQ)
- Duration of time to achieve a stable dose of SD-809, defined as the number of days from Day 1 until the first day at which the subject was taking the dose level they were receiving at Week 8.

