score, SDQ, UPDRS (speech) and the BARS scores) will also be presented by visit for the actual data and for the changes from Week 8 for the UHDRS parkinsonism subscore, the UHDRS cognitive exam scores, the behavioral assessment item scores and total score, the SDQ total score, the UPDRS dysarthria speech score, the HADS scores, the BARS scores, the ESS total score, and the MoCA[®] total score. Analyses of the UHDRS cognitive exam scores will be repeated excluding sites with conflict of interest or good clinical practice violations. Results of Questions 78 and 79 from the Clinical Summary section (Part VII) of the UHDRS will be summarized by visit using counts and percentages.

For C-SSRS, the number and percentage of subjects with suicidal ideation at any post-baseline time point (overall and by individual question), suicidal behavior at any post-baseline time point (overall and by individual question), suicidal ideation or behavior at any post-baseline time point (overall and by individual question), and self-injurious behavior without suicidal intent at any post-baseline time point will be presented for each treatment group. The number and percentage of subjects with suicidal ideation [affirmative ("YES") answer to questions 1 or 2 at any post-baseline time point], with suicidal behavior [affirmative ("YES") answer to questions 6, 7, 8 or 9 at any post-baseline time points], and who completed suicide [affirmative ("YES") answer to question 10 at any post-baseline time point] post-baseline will also be presented.

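### The C-SSRS is summarised only as any-post-baseline counts, so the ideation percentage cannot separate ideation already present at Baseline from new or worsened ideation

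*SAP*

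**What the plan says.** Protocol 8.4 lists among the safety endpoints "Observed values and changes in UHDRS, UPDRS (dysarthria), BARS, HADS, ESS, C-SSRS" and the MoCA. SAP 7.2 takes the C-SSRS out of its list of observed values and changes from baseline and gives it a line of its own: "Counts and percentages for Columbia Suicide Severity Rating Scale (C-SSRS").

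SAP 9.9.7 then describes two sets of C-SSRS counts.

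- The first covers ideation, behavior, either of these, and self-injury without suicidal intent. Behavior is summarised as "suicidal behavior at any post-baseline time point (overall and by individual question"), and the questions that make up the overall figure are not named.
- The second names its questions: "suicidal ideation [affirmative ('YES') answer to questions 1 or 2 at any post-baseline time point"]; subjects "with suicidal behavior [affirmative ('YES') answer to questions 6, 7, 8 or 9 at any post-baseline time points"]; and subjects "who completed suicide [affirmative ('YES') answer to question 10 at any post-baseline time point] post-baseline will also be presented".

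All of these counts are post-baseline. The same section exempts the C-SSRS from the change-from-baseline summaries given to the quantitative scales. SAP 8.10 lists two changes from the protocol, the compliance range and the move of TMC and total motor score to efficacy. The C-SSRS is not among them.

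On entry, Protocol 4.3 excludes a subject on this ground: "Subject has active suicidal ideation at Screening or Baseline". It also excludes previous intent with a specific plan (question 5), previous preparatory acts or behavior, and previous actual, interrupted or aborted attempts.

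**The concern.** A single-arm study has no concurrent control, so the subject's own baseline is the natural reference for a C-SSRS finding. Without it, a post-baseline percentage combines ideation that appeared or worsened on SD-809 with ideation the subject brought into the study. Suicidality matters enough in this plan to be an eligibility screen, a scheduled assessment at nearly every clinic visit and a named adverse event of interest. Because the study is descriptive, the tabulation rule determines the result that readers will see.

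There is also a traceability problem. A protocol endpoint expressed as change has become a count, and the section meant to record such changes does not mention it.

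**Working it through.** The plan states no C-SSRS event rate, so there is no figure to reproduce. The check sets the sections side by side and then sizes the effect on the planned numbers.

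**1. Is there any baseline comparison for the C-SSRS?**

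| Place | C-SSRS content |
|---|---|
| Protocol 8.4 | Observed values and changes |
| SAP 7.2 | Counts and percentages |
| SAP 9.9.7, first set | Any post-baseline time point |
| SAP 9.9.7, second set | Any post-baseline time point, by question number |
| SAP 9.9.7, change from baseline | C-SSRS exempted |
| SAP 8.10 | Not mentioned |

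No C-SSRS summary table uses baseline status. By contrast, SAP 9.9.6 plans shift tables for chemistry and hematology.

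**2. Can a subject enter with some ideation?** Protocol 4.3 bars active ideation at Screening or Baseline and, by history, intent with a specific plan, preparatory acts and attempts. It does not bar every positive ideation answer and does not tie the word active to question numbers. SAP 9.9.7 counts a yes to question 1 or 2 as ideation. A yes that the investigator did not regard as active at Baseline is therefore compatible with enrollment, and the same answer later counts as a post-baseline case.

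**3. Do the data exist?** Yes. In the schedules of events, Switch subjects have the Baseline version at Screening and the Since Last Visit version at Baseline. Rollover subjects bring the Week 13 C-SSRS from SD-809-C-15, with the Since Last Visit version used at all their visits. SAP 8.7 already defines the baseline value: the last pre-dose value for Switch, and the last off-treatment value (at least 4 days after the last dose) from Week 13 or Baseline for Rollover.

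**4. Size for ideation.** Input: planned N of about 116 (Protocol synopsis and Section 3). Let p be the share with lesser ideation at Baseline who report it again afterwards. The documents give no p, so this is an assumed range. Carried-over cases = p × 116.

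- p = 0%: 0 cases, and the planned count equals the count of new ideation.
- p = 3%: 0.03 × 116 = 3.5.
- p = 5%: 0.05 × 116 = 5.8.

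For p of 3% to 5%, about 3 to 6 of the counted cases are not new. That is 3/116 = 2.6 to 6/116 = 5.2 percentage points of the reported ideation percentage.

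**5. Size of the secondary point.** Suppose two subjects answer yes to one of questions 6 to 9, and a third dies by suicide with no such earlier answer.

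- Questions 6 to 9: 2/116 = 1.7%.
- Questions 6 to 10: 3/116 = 2.6%.
- Completed suicide on its own row: 1/116 = 0.9%.

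By cohort, one event is 1/80 = 1.3% in Rollover and 1/36 = 2.8% in Switch. The two behavior summaries in SAP 9.9.7 can therefore differ by these amounts, depending on whether the unnamed overall set includes question 10.

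**The case against.** The strongest case against is that eligibility already does most of the work. Active ideation and past attempts are excluded, so post-baseline behavior is largely new by design and only lesser ideation could carry over. If sites treat any positive answer as active, p is zero. Baseline C-SSRS values will also appear in subject listings (SAP 8.7), and the UHDRS suicidal-thoughts item and HADS depression score are summarised as changes from baseline (SAP 9.9.7). This limits the concern to ideation and makes its size uncertain. It does not replace a baseline display: listings are not summaries, and the other scales are different instruments.

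A second objection is that the baseline category is unclear because the form versions differ. SAP 8.7 settles which assessment counts, and both cohorts then use the Since Last Visit version at that point.

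Three stronger readings are tempting and should not be drawn.

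- *Suicides are captured only through an interview.* The protocol does say the "C-SSRS is an interview by trained study personnel". But SAP 9.9.1 has completed suicide as a preferred term in the Suicidality group, counts fatal TEAEs, and lists SAEs and fatal adverse events. The public appendices carry only the titles of the C-SSRS forms, so whether question 10 can be completed without the subject cannot be judged.
- *A suicide lowers the behavior count.* It leaves the count for questions 6 to 9 unchanged, and completed suicide is reported beside it in the same sentence.
- *The study has no other reference for suicidality.* SAP 9.9.1 gives exposure-adjusted Suicidality adverse event rates for the active and placebo groups of SD-809-C-15 as well as both C-16 cohorts.

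**Conclusion.** The baseline point holds. As planned, the C-SSRS ideation percentage cannot be read as new or worsened ideation, and the move from the protocol's changes to post-baseline counts is not recorded in SAP 8.10. The effect runs from none to about 3 to 6 subjects of 116 under the assumed range of 0% to 5%. It rests on some ideation at Baseline being judged not active, which the criteria permit but the documents do not quantify.

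The behavior point is secondary. The overall question set is undefined rather than shown to exclude question 10, and completed suicides are reported separately. What is missing is a stated definition and a cross-check with the adverse event and death data. Such a check is useful because the exposure-adjusted adverse event rate omits events after the last dose, while the period-based counts include follow-up events.

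No hypothesis test is affected, since SAP 8.1 plans none. This is a reporting weakness worth correcting, and it does not threaten the study's validity.

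**What to change.** In SAP 9.9.7:

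1. Tabulate the C-SSRS at Baseline as defined in SAP 8.7.
2. Add, for each cohort, a shift from Baseline category to worst post-baseline category, with counts of new and of worsened ideation beside the planned counts. State how the categories are ordered. Note that the worst of many visits is compared with a single baseline assessment, so these counts tend to grow with follow-up.
3. State that overall suicidal behavior covers questions 6 to 10, and keep completed suicide as its own row as well.
4. Cross-check question 10 against adverse event and death records, and explain any mismatch in the report.
5. Replace the reference to treatment groups with the cohorts, which SAP 8.7 already makes the default.

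In SAP 8.10, record the change from observed values and changes to counts with a baseline shift.

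The cost is SAP wording and one extra table per cohort. The data are already collected. The behavior percentage may rise slightly if a suicide occurs, and the ideation display will be somewhat longer.
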